3.3. OBJECTIVES

The Primary Objective of this study is safety of the Investigational Product, hCT-MSCs.

The primary endpoint is safety measured by:

- 1. Incidence of infusion reactions
- 2. Incidence of later reactions attributed to the investigational product Formation of new anti-PRA antibodies

The Secondary Objective of this study is to describe the potential for MSC therapy to favorably alter the course of COVID-ARDS. Endpoints are:

- 1. Time to recovery, defined as discharge from the hospital (alive) or remaining in the hospital without the need for supplemental oxygen or other COVID-related medical care.
- 2. Increase in PaO2/FiO2 ratio by 50% by Day 4 (96 hours after first infusion). PaO2/FiO2 may be calculated from an arterial blood gas or imputed from the SpO2/FiO2 table (Brown, et al. Chest 2016).
- 3. Days to hospital discharge to home
- 4. # of ventilator free days
- 5. # of days requiring O2 support
- 6. Feasibility of accrual to the randomized portion of this study

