2. PROTOCOL SYNOPSIS

This is a 50 patient, Phase 1/2a multi-center pilot study to test the safety and to describe the preliminary efficacy of intravenous administration of allogenic human cord tissue mesenchymal stromal cells (hCT- MSC) as an investigational agent, under U.S. INDs 19968 (Duke) and 19937 (U Miami) to patients with acute respiratory distress syndrome (ARDS) due to COVID-19 infection (COVID-ARDS). Patients will be eligible for treatment with 3 daily consecutive doses of hCT-MSC at 1 million cells/kg (max dose 100 million cells) in the phase 1 portion of the study or a fixed dose of 100 million cells daily x 3 days, 12-36 hours apart in the phase 2 portion of the study, if they have a

Confidential Page 8 of 32

confirmed diagnosis of COVID-19 and meet clinical and radiographic criteria for ARDS. The primary endpoint is short-term safety of hCT-MSC infusions given on this schedule. The key secondary endpoints are 28 day survival, an increase in PaO2/FiO2 ratio by 50% at 96 hours, days to hospital discharge to home or rehab, and number of days requiring mechanical or non-invasive ventilation or high flow nasal cannula.

The study will be executed in two phases. The first 10 consecutive patients will all receive investigational product. The second part of the study is a randomized, controlled trial in 40 additional patients. The overall aim of the study is to establish safety and to gain critical information as to whether patients with COVID-ARDS will benefit from MSC infusions. Results from the first 10 patients will be compared with concurrent outcomes utilizing standard of care treatments in participating hospitals and in published reports in the medical literature. Results from the additional 40 patients will be analyzed as a randomized placebo control trial. The trial is relying on focused eligibility of the participants (patients with ARDS), single cohort with short trial time (4 weeks), and simple assessment of clinical outcome (survival, improvement of ARDS). This is a sequential design in the sense that after the first 10 patients are evaluated a decision will be made by the PIs and the Data Safety Monitoring Board whether to proceed with the exploratory randomized portion of the study.

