6.1.1. LABORATORY AND CLINICAL EVALUATIONS

- Baseline is at enrollment (within 3 days- excluding COVID-19 PCR test which can obtained within 90 days to avoid repeat testing). Days post infusion are calculated from the first infusion. The "*" signifies that the test results from standard of care testing will be used however, they do not need to be obtained specifically for the study
- Height and weight with baseline physical examination
- Hematology: hemoglobin, hematocrit, platelet count, white blood cell (WBC) count, and WBC differential at baseline, day of infusion, Day 4, Day 7*, and Day 28*
- Coagulation: prothrombin time (PT)/aPTT/INR, D-dimer at baseline, Day 4*, and Day 28*
- Serum chemistry: CRP, ESR, AST, ALT, LDH, total bilirubin, alkaline phosphatase, total protein, albumin, sodium, potassium, chloride, carbon dioxide, calcium, blood urea nitrogen (BUN), creatinine, creatinine clearance and glucose at baseline, day of infusion*, Day 4*, Day 7*, and Day 28*
- Urinalysis*: pH, specific gravity, protein, glucose, ketones, blood, leukocyte esterase, and nitrite at baseline. Microscopy required only to follow-up clinically significant abnormal findings
- Chest x-ray* at baseline, Day 4*, Day 7*, and Day 28*
- ABGs prior, 1-4 hours after, Day 4*, Day 7*, and Day 28*
- COVID-19 PCR at baseline (do not repeat testing if obtained within 90 days of enrollment), day
 4*, 7*, and 28* post treatment
- Donor referral panel at baseline
- HLA typing (high resolution class I and class II) at baseline
- PRA (Anti-HLA antibodies) at baseline and day 28
- PaO2/FiO2 and oxygenation index endpoints (based on invasive or non-invasive mechanical ventilation or high flow nasal cannula use). To be done at Baseline, Day 1, Day 2, Day 4, and if on continued ventilation Day 7, and Day 14. PaO2/FiO2 may be calculated from an arterial blood gas or imputed from the SpO2/FiO2 table (Brown, et al. Chest 2016)
- Day 28 mortality
- Hospital discharge
- Invasive or non-invasive mechanical ventilation-free days and oxygen-free days
- Lung injury severity score (Murray) at Baseline, Day 1, Day 2, Day 4, Day 7, and Day 14. The
 most recent chest x-ray will be used to calculate the Murray score. For patients on pressure
 support mode ventilation, the peak pressure will be used in place of the plateau pressure to
 calculate compliance
- Any laboratory or imaging can be repeated outside the protocol requirements at the discretion of the treating physicians

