7 TREATMENT VISIT SCHEDULE

Evaluation	Baseline (within 3 days)	Infusion Days ⁱ	Day 4	Day 7 (+ 1 day)	Day 14 (+ 2 days)	Day 28 (+2 days) -	Day 90 (+ 5 days)
Informed Consent	Х						
Medical History, height, weight, and Demographics	х						
Physical Exam	Х	Xj	Х	Х			
Vital Signs ^a	Χ	X ^{bj}					
Hematology ^c	Х		Х	X*		X*	
Serum Chemistry d	Х	X*	Χ*	X*		X*	
Coagulation ^e	Х		X*			X*	
Pregnancy Test ^f	Х						
EKG	X*						
Urinalysis	X*						
HLA Typing	Х						
PRA	Х					Х	
Donor screening panel	Х						
COVID PCR	Х		Χ*	X*		X*	
Chest x-ray	Х*		Χ*	X*		X*	
ABG	Х	Xgj	Χ*	X*		X*	
Pre-medications		Χj					
Concomitant Meds	X	X	Х	X		Х	
Adverse Events Assessment		X	Х	X			Х
Lung Injury Severity Score (Murray)	х	Xı	Х	Х	X	Х	

LAR

Confidential Page 22 of 33

hCT-MSC Infusion		Xh					
PaO2/FiO2	Х	Xj	Х	Х	X		
Prone Ventilation ^k	Х	Х	X	Х			
Neuromuscular				X			
blocker ^k	X	X	X				
Inhaled nitric acid ^k	Х	Х	X	Х			
Inhaled				X			
epoprostenaol ^k	X	X	X				
Corticosteroids ^k	X	X	X	X			
Survival						X	Х
Oxygen use							X ^m

- a. Blood Pressure, Heart Rate, Respiratory Rate, Temperature, and O₂ Saturation
- b. Vitals are taken prior to pre-medications, prior to infusion, every 15 minutes during infusion, every 30 minutes post infusion X 2, then hourly X 4.
- c. Hematology: Hemoglobin, Hematocrit, platelet count, White Blood Cells, and differential
- d. Chemistry: CRP, ESR, AST, ALT, LDH, total bilirubin, alkaline phosphatase, total protein, albumin, sodium, potassium, chloride, carbon dioxide, calcium, blood urea nitrogen, creatinine, creatinine clearance, glucose
- e. Coagulation: Prothrombin Time (PT)/aPTT/INR, D-dimer
- f. Pregnancy Test (WOCBP) Women of Child Bearing Potential. If done prior to baseline as part of hospitalization, this does not need to be repeated.
- g. ABGs to be done prior to infusion, and 1-4 hours after each infusion
- h. Three infusions will be given on days 1, 2 and 3.
- i. All Days will be calculated from the first infusion, or Day 1.
- j. These elements will be done on Day 1, Day 2, and Day 3. Premedications, and vital signs will also be done at each infusion. Physical exams will be done daily during hospitalization and data will be pulled from those clinical notes.
- k. Monitor the use, duration, and if applicable, the dose during hospitalization
- I. Only SAEs are gathered at Day 90
- m. If use of oxygen is required at Day 90 will be documented
- n. Day 28 is the time the primary endpoint will be evaluated.

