9.1.2 PHASE II

The second phase of the study will randomize 20 patients to placebo and 20 to hCT-MSC. The primary utility of the randomized phase of the trial is to evaluate the feasibility of conducting a larger, randomized trial comparing hCT-MSC to placebo, and to conduct descriptive analyses of efficacy outcomes. To enroll and randomize 90% of the eligible patients screened is a positive indicator of feasibility. The primary efficacy outcome of interest is time to recovery, defined as discharge from the hospital (alive) or remaining in the hospital without the need for supplemental oxygen or other COVID-related medical care. We expect based on previous research that 30% of patients in the placebo arm will recover at Day 28. This study is not powered to detect differences between arms except when those differences are large. Therefore, the approach to analysis will be descriptive. For example, with 20 patients per arm and no losses to follow-up, a 365-day accrual period and 28 days of follow-up per patient, the study would have 54% power to detect a doubling in the hazard of recovery with treatment (hazard ratio = 2.0) and 76% power to detect a hazard ratio of 2.5 using a log-rank test with 2-sided Type I error of 5%.

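### Time to recovery counts any live hospital discharge as recovery, so a patient discharged to hospice is scored as recovered, and no rule covers transfer to another facility.

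*Combined protocol and SAP*

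**What the plan says.** Section 3.3, item 1 of the secondary endpoints, reads "Time to recovery, defined as discharge from the hospital (alive) or remaining in the hospital without the need for supplemental oxygen" and adds other COVID-related care to the oxygen condition. Section 9.1.2 repeats the definition and gives it its standing in Phase II: "The primary efficacy outcome of interest is time to recovery, defined as discharge from the hospital (alive) or remaining in the hospital", followed by the same condition. The trial's primary endpoint is safety, so this is the lead efficacy outcome and not the primary endpoint of the study.

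A destination is named only for a different endpoint. The synopsis lists "days to hospital discharge to home or rehab"; section 3.3, item 3, lists "Days to hospital discharge to home".

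Section 6.1.1 lists "Hospital discharge" as a data item, with no destination and no record of respiratory support on leaving. In the section 7 schedule, the oxygen-use row is marked only at the last visit: "If use of oxygen is required at Day 90 will be documented". Section 9.4 plans Kaplan-Meier plots of cumulative recovery by arm and gives no scoring rule for hospice or transfer.

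**The concern.** The two limbs of the definition set different standards. A patient who stays must need neither oxygen nor further COVID-related care. A patient who leaves must only be alive. A discharge to hospice is a treatment failure, yet it meets the second standard on the day it happens. In a time-to-first-event analysis that score is permanent: a hypothetical patient discharged to hospice on Day 12 who dies on Day 15 remains a Day 12 recovery.

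Such exits are plausible here. Section 4.1 admits patients with ARDS on mechanical or non-invasive ventilation or high flow, and the synopsis cites 30-60% mortality for ARDS. The study is multi-center, so local discharge and transfer practice could also affect the outcome. At stake is whether the recovery curve, which is meant to inform a larger trial, describes recovery.

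**Working it through.** **1. Reading the definition.** The words on oxygen and COVID-related care follow, and qualify, remaining in hospital. The discharge limb carries one condition, being alive. The other places that could narrow it do not:

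- Section 6.1.1 lists discharge without a destination.
- The section 7 schedule has no destination item.
- Section 9.3 (intention to treat) governs which arm a patient is analysed in, not what counts as an event.
- Section 9.4 has no rule for hospice or transfer.
- The home or rehab wording belongs to the separate days-to-discharge endpoint.

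Hospice discharge therefore counts as recovery directly from the text. Transfer is different: no section says whether moving to another facility is a discharge from the hospital. It is neither included nor excluded.

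**2. The plan's own figures for this outcome.** Section 9.1.2 gives 20 per arm, 30% placebo recovery at Day 28, and log-rank power of 54% at a hazard ratio of 2.0 and 76% at 2.5. With exponential recovery times, the placebo hazard is −ln(0.70)/28 = 0.0127 per day. Simulation (20,000 runs) with uniform 365-day accrual and every patient followed to study end gives 52.4% and 75.9%, close to the stated values. With 28 days per patient, as the same sentence says, it gives 27.8% and 46.7%. That mismatch is a separate matter and does not decide this point.

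**3. Weight of one exit.**

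- Expected placebo recoveries: 0.30 × 20 = 6.
- One patient in an arm of 20: 1/20 = 5 percentage points, and 1/6 of the expected placebo recoveries.
- Section 9.4 also compares each product arm of 10 with placebo; there one patient is 1/10 = 10 percentage points.

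**4. Effect on the hazard ratio if exits are equally frequent in both arms.** Let q be the share of the placebo recovery hazard λ that comes from such exits, with treatment leaving their rate unchanged. Then

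observed HR = [HR × λ(1 − q) + λq] / λ = HR − q(HR − 1).

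For a true HR of 2.0 this is 2 − q. The documents give no value for q; 5% to 30% is an assumed range.

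| q | Such exits among 6 placebo recoveries | Observed HR, true 2.0 | Placebo recovery if none is counted |
|---|---|---|---|
| 5% | 0.3 | 1.95 | 28.5% |
| 10% | 0.6 | 1.90 | 27% |
| 20% | 1.2 | 1.80 | 24% |
| 30% | 1.8 | 1.70 | 21% |

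The last column is 30% × (1 − q). The whole range corresponds to fewer than two placebo patients.

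**The case against.** Phase II is descriptive. Section 9.1.2 says it is not powered except for large differences, and no decision rule depends on recovery. The synopsis and section 3.2 make 28-day survival a key secondary endpoint, and discharge to home and ventilator-free days are reported separately, so an early death after hospice discharge would be visible elsewhere. Section 4.2 excludes shock, moribund patients and ECMO, which removes some of the sickest. All of this stands and limits the harm. None of it changes how recovery is scored.

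Two stronger readings are tempting and should not be made.

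- A reader might infer that a patient transferred while still ventilated is scored as recovered. The documents are silent on whether a transfer is a discharge, so this is a possible literal reading and not a stated rule.
- A reader might infer a spurious benefit, for example two such exits in the treated arm alone adding 2/20 = 10 percentage points. Phase II is randomised and blinded, and the documents give no reason for imbalance beyond chance. With equal rates the result is dilution. The expected 30% may also already include such exits, because the definition used in the earlier research behind it is not shown.

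**Conclusion.** The point holds. As written, sections 3.3 and 9.1.2 score a discharge to hospice as recovery, and they leave inter-facility transfer unscored. For hospice this is a rule that gives a wrong result, not merely missing detail; for transfer it is a gap.

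Each such exit moves a 20-patient arm by 5 percentage points. Under equal frequency across arms, a true hazard ratio of 2.0 would be seen as about 1.95 to 1.70. That rests on an assumed share of 5% to 30% of counted placebo recoveries, constant hazards, and no treatment effect on the exits. The actual frequency is unknown and could be zero. Because Phase II is descriptive and survival is reported alongside, this is an endpoint definition to correct, not a threat to the trial's safety objective.

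**What to change.** In section 3.3, item 1, and section 9.1.2, add:

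- Discharge to hospice is not recovery. These patients are kept as not recovered through Day 28 and are not censored at discharge. Censoring would treat them as having the same later chance of recovery as patients still under care.
- Transfer to another acute or long-term acute care facility is continued hospitalization. Recovery is dated when the patient meets the existing no-oxygen, no-COVID-care condition, or is discharged from that facility other than to hospice.

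Record discharge destination with the hospital-discharge item in section 6.1.1; the days-to-discharge-home endpoint already needs it. For transferred patients, obtain the date of recovery or discharge, not only current status, at the existing Day 28 follow-up (section 6.1.2), because a time-to-event outcome needs the date.

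Cost: protocol wording, one data field, some follow-up for the few transferred patients, and possibly a slightly lower recovery proportion than the 30% assumed. A patient discharged home on oxygen would still count as recovered. This change leaves that choice as it is.

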9.4 ANALYSIS PLAN

Baseline characteristics of the participants will be summarized by study phase. The proportion of patients with infusion-related reactions and other unexpected product- related adverse reactions will be tabulated descriptively using CTCAE terminology. For Phase II, the time to recovery will be described using Kaplan-Meier plots comparing cumulative incidence in participants randomized to hCT-MSC with placebo. Results will be analyzed two ways: combining the two hCT-MSC arms vs. placebo, and each hCT-MSC arm separately vs. placebo. Other continuous, ordinal and binary outcomes will be analyzed in a similar fashion using appropriate descriptive statistics.

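### PaO2/FiO2 is scheduled at baseline and Day 4, but its only efficacy outcome with a defined summary measure is a yes/no 50% rise, so the 20-versus-20 oxygenation estimate will be less precise than the data allow

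*Combined protocol and SAP*

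**What the plan says.** The efficacy outcome for oxygenation is a threshold wherever it is defined. Section 3.3 (Objectives) lists "Increase in PaO2/FiO2 ratio by 50% by Day 4", timed at 96 hours from the first infusion, among the secondary endpoints. The synopsis (section 2) names "an increase in PaO2/FiO2 ratio by 50% at 96 hours" as a key secondary endpoint, and section 3.2 repeats it. No reason for choosing 50% is given.

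The underlying ratio is collected well beyond what the threshold needs. Section 6.1.1 schedules it as follows: "To be done at Baseline, Day 1, Day 2, Day 4, and if on continued ventilation Day 7, and Day 14". The table in section 7 agrees on baseline and Day 4. The 6.1.1 entry opens with "PaO2/FiO2 and oxygenation index endpoints", so the undichotomised ratio is called an endpoint there, but no summary measure or comparison is attached. On the source of the value, section 3.3 says "PaO2/FiO2 may be calculated from an arterial blood gas or imputed from the SpO2/FiO2 table".

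Section 9.1.2 sets the size of the comparison: "The second phase of the study will randomize 20 patients to placebo and 20 to hCT-MSC". It describes the analysis as descriptive. Section 9.4 does not mention PaO2/FiO2. It covers everything other than safety and time to recovery in one sentence: "Other continuous, ordinal and binary outcomes will be analyzed in a similar fashion using appropriate descriptive statistics".

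**The concern.** Followed as written, the defined outcome yields one percentage per arm. A patient whose ratio rises 49% counts the same as one who deteriorates. The hurdle also depends on the starting point. Eligibility admits any ratio up to 300, so a patient starting at 100 needs 100 × 1.5 = 150, still within the entry range, while one starting at 290 needs 290 × 1.5 = 435. With 20 per arm, a chance imbalance in baseline can move the responder comparison, and nothing in 9.4 adjusts for it.

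Section 9.1.2 says the randomised phase is there to judge the feasibility of a larger trial and to describe efficacy. A later trial could use an estimated ratio with its interval, its SD and its correlation with baseline. A responder count supplies neither the SD nor the correlation. A continuous summary is allowed under 9.4 but not named, so its form could be chosen after the data are seen.

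**Working it through.** The plan gives no power or precision figure for this outcome, so there is none to reproduce. The 54% and 76% in 9.1.2 concern time to recovery.

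**Inputs from the documents:** 20 versus 20 (9.1.2); a 50% rise (3.3); two-sided 5%, borrowed from the log-rank example in 9.1.2. **Assumed, because the documents give no figures:** normal log PaO2/FiO2, SD 0.35-0.45, baseline-to-Day-4 correlation 0.4-0.6, a 15% rise in both arms, and a further 35% or 20% from treatment. The rise is read as Day 4 over baseline.

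**Step 1: the cut alone, without baseline adjustment.** Efficiency of a normal variable cut at responder rate p, relative to its mean, is φ(z_p)² / [p(1−p)].
- p = 20%: 0.280² / 0.16 = 0.49; 20 × 0.49 = 9.8 per arm
- p = 30%: 0.348² / 0.21 = 0.58; 11.5 per arm
- p = 40%: 0.386² / 0.24 = 0.62; 12.4 per arm
- p = 50%: 0.399² / 0.25 = 0.64, the maximum; 12.7 per arm

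**Step 2: one setting in full (SD 0.35, correlation 0.4, 35% effect).**
- SD of the log change: 0.35 × √(2 × 0.6) = 0.383. The threshold is ln 1.5 = 0.405.
- Placebo mean ln 1.15 = 0.140, so the responder rate is 1 − Φ(0.266/0.383) = 24.4%. Treated mean 0.140 + 0.300 = 0.440, so 53.6%.
- Responder difference 0.292, SE √[(0.244 × 0.756 + 0.536 × 0.464)/20] = 0.147. The 95% CI is about ±29 points.
- Adjusted log ratio 0.300, SE 0.35 × √(1 − 0.16) × √(2/20) = 0.101. With t(37) = 2.026 the half-width is 0.206, so a ratio of 1.35 has a CI of about 1.10 to 1.66.
- Power: responders, Φ[(0.292 − 1.96 × 0.154)/0.147] ≈ 47%, where 0.154 is the pooled SE; model, noncentral t with 0.300/0.101 = 2.96, about 82%.

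**Step 3: the same formulas in all four settings, 35% effect.**

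| SD | Correlation | Responder rates | Effect/SE, responder | Effect/SE, model | Power, responder | Power, model |
|---|---|---|---|---|---|---|
| 0.35 | 0.4 | 24% v 54% | 1.98 | 2.96 | 47% | 82% |
| 0.35 | 0.6 | 20% v 54% | 2.42 | 3.39 | 63% | 91% |
| 0.45 | 0.4 | 30% v 53% | 1.54 | 2.30 | 32% | 61% |
| 0.45 | 0.6 | 25% v 53% | 1.89 | 2.64 | 44% | 73% |

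Simulation (6,000 trials per setting) agrees within about two points: 31-64% for responders and 60-90% for the model. With no treatment effect both reject in about 5% of trials, so the gain is not inflated error. At a 20% effect the simulated ranges are about 16-29% and 25-50%.

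**Step 4: early deaths.** Suppose 10% die before Day 4 in each arm, with a 35% effect. Responders with deaths as failures have about 29-57% power. A baseline-adjusted rank analysis with deaths ranked worst has about 38-60%. The rank analysis stays ahead in every setting, by much less than in step 3.

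**The case against.** **Nothing is discarded, and this is not the only oxygenation outcome.** A reader might infer from 3.3 that oxygenation is measured only by the threshold. The documents do not support that. Section 6.1.1 names the undichotomised ratio and the oxygenation index as endpoints and schedules the Murray score; 3.3 also lists ventilator-free days and time on oxygen support. The raw values are kept, and 9.4 would permit a continuous summary by arm. What stands is narrower: the threshold is the only PaO2/FiO2 efficacy outcome with a defined summary measure.

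**Power is the wrong yardstick.** A reader might infer that the trial is underpowered on a test it plans. It plans none here. The outcome is secondary, the analysis is descriptive, and 9.1.2 makes time to recovery the main efficacy outcome. The power figures serve only as a stand-in for precision.

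**The size is wholly assumed.** This stands. At a 20% effect neither analysis does well. The gap in step 3 also combines two gains, avoiding the cut and adjusting for baseline; step 1 isolates the first.

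**A continuous model handles death and recovery badly.** This stands too. A patient who dies before Day 4 has no value, whereas a responder outcome can count death as failure. Section 6.1.1 ties the ratio to ventilation or high-flow use, and Day 4 blood gases come from routine care only. In a deliberately adverse illustration (mean baseline 150, 10% early deaths, and Day 4 values above 300 missing from the model because support has stopped but credited as responses when the rise reaches 50%), model power falls to 30-67% against 28-58% for responders. The estimated ratio shrinks from 1.35 to 1.21-1.26. The SpO2 imputation could recover some of those values, but an explicit rule is needed.

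**The baseline-dependent hurdle is not bias.** Randomisation balances baseline in expectation, so the 150-versus-435 contrast shows unequal difficulty and sensitivity to chance imbalance, no more.

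**Conclusion.** The point holds as a recommendation about precision. PaO2/FiO2 is scheduled at baseline and Day 4, the only defined efficacy summary of it is a yes/no cut, and 9.4 commits to no baseline-adjusted estimate or interval. Under normality the cut costs at least 36% of the information (1 − 0.64), and 51% at a 20% responder rate (1 − 0.49). That result needs no assumed effect size. The larger advantage of the adjusted model rests on assumed SD, correlation, background rise and effect, and on nearly complete Day 4 data; it shrinks to a modest gain once early deaths are ranked worst. The change is worth making because it uses data already scheduled. It does not call the trial's validity or its primary safety objective into question.

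**What to change.** Amend section 9.4 before unblinding:

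1. Keep the 50% responder proportion, and state that deaths before Day 4 count as non-responders.
2. Add the between-arm ratio of Day 4 PaO2/FiO2 from a linear model of log Day 4 ratio on arm and log baseline, with a 95% CI. Label it as an estimate among patients alive with a Day 4 value.
3. Report beside it a baseline-adjusted rank analysis of all randomised patients, with deaths before Day 4 given the worst rank. This keeps to the intention-to-treat principle in 9.3.
4. For patients off ventilatory support, or without a Day 4 blood gas, use the SpO2/FiO2 imputation the protocol already allows, and report by arm how many values were imputed.

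The cost is one extra model with its companion rank analysis, and a stated rule for early deaths. No visit, test or patient is added. The model in item 2 describes survivors with a value and should not be read without item 3.
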